Précis: The Moderate Alcohol and Cardiovascular Health Trial (MACH15) is a multicenter, worldwide, randomized clinical trial of ~15 g of alcohol daily versus abstinence, using a balanced parallel design and single-blind assessment of all outcomes among approximately 7,800 participants aged 50 years and older with above-average cardiovascular risk. Intervention will average 6 years in duration with a common close-out date. Following recruitment and pre-screening, participants will attend a screening visit followed by a two-week abstinence washout period, a baseline visit and randomization, and subsequent visits at 3 months, 6 months, 12 months, and then annually until close-out.

Objectives: **Primary Trial Objective:** To determine the effects of one serving of alcohol (~15 g) daily compared to no alcohol intake on the risk of incident cardiovascular disease among adults at above-average cardiovascular risk.

Secondary Trial Objective: To determine the effects of one serving of alcohol (~15 g) daily compared with no alcohol intake on the risk of incident diabetes among participants free of diabetes at baseline.

Endpoints

Primary Outcome:

Time from baseline to a composite endpoint comprised of the first occurrence of a non-fatal myocardial infarction, non-fatal ischemic stroke, hospitalization for angina, coronary/carotid revascularization, or all-cause mortality.

Secondary Outcomes:

1. Time from baseline to a composite endpoint comprised of the first occurrence of a non-fatal myocardial infarction, non-fatal ischemic stroke, hospitalization for angina, coronary/carotid revascularization, or cardiovascular death.
2. Progression among normoglycemic and pre-diabetes individuals to American Diabetes Association (ADA)-defined diabetes.

Tertiary Outcomes:

1. Time from baseline to a composite endpoint comprised of the first occurrence of a non-fatal myocardial infarction, non-fatal ischemic stroke, or cardiovascular death.

2. Time from baseline to the first occurrence of each of the components of primary outcome (5 outcomes).
3. Time from baseline to cardiovascular death.
4. Progression among normoglycemic individuals to ADA-defined prediabetes.

Population:	Adults aged 50 and older at above-average cardiovascular risk
Phase:	Phase III
Number of Clinical Sites Enrolling Participants:	~20 clinical sites worldwide (North and South America, Asia, Australia, Europe, Africa)

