There are numerous risk factors for CVD and diabetes, and these will be measured at baseline and at subsequent visits, including age, body mass index, hemoglobin, blood pressure, gender, race/ethnicity, healthy lifestyle, and other co-morbidities. Although randomization ensures that, on average, treatment groups will be balanced with respect to all of these factors, this may not be true in the given trial. Thus, we will assess the success of randomization by first comparing the baseline characteristics of participants in the treatment groups, and then re-assess treatment effects in secondary analysis after adjusting for the risk factors associated with the strongest imbalances. To adjust as finely as possible for confounding by measured risk factors, an additional secondary analysis will be conducted that adjusts for all measured risk factors.

Non-adherence to the assigned treatment is another potential challenge to power an unbiased treatment effect estimation that we will address in secondary sensitivity analysis by conducting *per protocol* and *as treated* analyses,⁸ by using instrumental variables methods,^{9,10} by potential outcomes

approaches,¹¹ by comparing the compliance estimates and by computing log rank tests weighted by time-varying probability of adherence.¹² *Per protocol* analysis excludes non-compliant participants from their respective arms. *As treated* analysis ignores treatment assignment but, rather, analyzes participants according to the amount of alcohol intake reported, regardless of what was assigned. The “contamination-adjusted intention-to-treat” uses instrumental variable analysis to address non-adherence in a two-stage approach. The potential outcomes approach is an estimation procedure for the intention-to-treat effect that maintains randomization-based properties under more plausible, non-ignorable noncompliance and non-ignorable missing-outcome conditions. The log rank tests weighted by time-varying probability of adherence involves modeling the probability of non-adherence given available covariate data, and then uses the inverse of these estimated probabilities, suitably stabilized, to reweight the log rank test statistic to mimic the study population that would have been observed, had there been no non-adherence

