8.2 SAMPLE SIZE CALCULATIONS

Sample size calculations involved extensive explorations over a range of primary endpoint definitions and baseline rates, baseline adherence rates and improvements to these due to household network effects, proportions of households with 1, 2 and 3 eligible members, intra-household correlation coefficients, and minimum expected effect sizes.

We originally assumed that our trial will be individually randomized trial, and that the primary combined expanded CVD incidence endpoint in the abstention arm will have a rate of 0.026/person-year, modestly higher than the 2.2% annual rate observed in SPRINT,¹⁵ increased slightly because, unlike SPRINT, we are including diabetic individuals and total mortality as an outcome and excluding CHF alone. Participants will enroll during the first 3 years and then will be followed for an average of 6 years. We have assumed that there will be 1% annual loss to follow-up (LTF) in both groups, and 10% non-adherence at any point in time over follow-up for participants who are the sole person in their household to be randomized, leading, for these participants, to an effective hazard ratio of 0.838 under an assumed true hazard ratio of 0.82 as in Ronksley, et al.¹⁶ Under these assumptions, to provide a minimum of 80% power at a two-sided 0.05 significance level for detecting a 18% relative decrease in the intervention group endpoint rate, for an individually randomized trial design with one participant per household, we will need 3,900 participants per arm,¹⁷ for a total of 7,800.

Although we conservatively powered the trial for an expected relative risk (RR) of 0.82, there is substantial evidence suggesting that for CVD, an RR of 0.75 is likely to be observed. If so, we will have adequate power for baseline rates as low as approximately 0.0125/person-year, significantly lower than the observed rate in MESA.

[figure not shown]
TABLE 8.1: POWER FOR CARDIOVASCULAR DISEASE ANNUAL EVENT RATES

Annual Event Rate	Relative Risk		
	RR=0.82	RR=0.80	RR=0.75
1.4%	55%	65%	84%
1.8%	65%	75%	92%
2.2%	74%	83%	96%
2.6%	80%	88%	98%
3.0%	85%	92%	99%
3.4%	89%	94%	99%

Figure 8.1 presents power for different values of relative risks (0.80, 0.82 and 0.84) as a function of a range of plausible annual events rates (from 0.014/year to 0.035/year).

FIGURE 8.1: POWER FOR PRIMARY ENDPOINT

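### The adherence-weighted log-rank sensitivity analysis is specified with the inverse of the probability of non-adherence, which contradicts its own name and aim

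*Combined protocol and SAP*

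**What the plan says.** Section 8.1.1 makes the intention-to-treat comparison primary and then lists several supporting analyses for non-adherence: per-protocol, as-treated, instrumental-variable, potential-outcomes and, last, a reweighted test. The last is introduced as addressing non-adherence "by computing log rank tests weighted by time-varying probability of adherence". The section later explains that this method "involves modeling the probability of non-adherence given available covariate data, and then uses the inverse of these estimated probabilities, suitably stabilized". The same sentence gives the purpose: the reweighted data should stand for the trial population as it would have looked if nobody had departed from assignment.

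No other part of the document gives a weight formula, the stabilizing numerator, the covariates, a truncation rule, or a definition of non-adherence for this analysis. The section cites a methods paper for the test but does not reproduce its formula.

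**The concern.** In the explanatory sentence, the only probability to which the inversion can refer is that of non-adherence. To represent full adherence, people who are still adherent but resemble those who stopped must count for more, so that they stand in for them. That requires the inverse of the probability of having remained adherent. Inverting the probability of stopping does the opposite: the most reliable adherers get the largest weights.

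If stopping is related to prognosis in one arm more than in the other, the reweighted arms no longer have comparable risk, and a difference can appear when alcohol has no effect. Section 7.4.5 makes such a pattern plausible. It lists incident illnesses for which the intervention is discontinued, at least temporarily, and this changes behaviour mainly in the alcohol arm. A programmer who follows the text would compute the wrong estimator, and a correction made after unblinding would look data-driven.

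**Working it through.** **1. The plan's own figures.** The document gives no number for the weighted analysis. The design effect is the natural yardstick, so it was reproduced first. Section 8.2 assumes "1% annual loss to follow-up (LTF) in both groups, and 10% non-adherence at any point in time over follow-up" and an "effective hazard ratio of 0.838 under an assumed true hazard ratio of 0.82":

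0.9 × 0.82 + 0.1 × 1 = 0.838, as stated.

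The abstention-arm endpoint "will have a rate of 0.026/person-year", and the design is "to provide a minimum of 80% power at a two-sided 0.05 significance level". Schoenfeld's formula gives 4 × (1.960 + 0.842)² / (ln 0.838)² ≈ 1,006 events. With 1% annual loss and follow-up uniform over 4.5 to 7.5 years, that means 7,774 participants (7,812 by Freedman's formula), against 7,800 stated ("we will need 3,900 participants per arm"). Power at 7,800 is 80.2%. The design figures hold.

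**2. Direction of the weights.** Take two people with non-adherence probabilities of 5% and 40% (illustrative values).
- As written: 1/0.05 = 20 and 1/0.40 = 2.5, a ratio of 8 to 1 for the reliable adherer.
- For the stated aim: 1/0.95 = 1.05 and 1/0.60 = 1.67, a ratio of 0.63 to 1.

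A stabilizing numerator that depends only on arm and time multiplies everyone at risk in an arm by the same factor, so the order stays reversed.

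**3. Size under a true hazard ratio of 1.** The inputs are assumptions: a risk factor with 30% prevalence, event hazard ratio k = 1.5 to 3, and stopping r = 1.5 to 3 times as frequent in those who have it. Mean non-adherence was set at 10%, which is the only one of these inputs with a counterpart in Section 8.2.

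With literal weights proportional to 1/r in the high-risk group, an arm's weighted hazard, relative to the low-risk hazard, is approximately

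H(r) = (0.3k/r + 0.7) / (0.3/r + 0.7), and H(1) = 0.3k + 0.7.

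The spurious hazard ratio is H(r in alcohol arm) / H(r in abstention arm). For k = 2.5 and r = 3 in the alcohol arm only: (0.25 + 0.70)/(0.10 + 0.70) = 1.1875; H(1) = 1.45; ratio 0.82.

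| k | r = 1.5, alcohol arm only | r = 2, alcohol arm only | r = 3, alcohol arm only | r = 2, abstention arm only |
|---|---|---|---|---|
| 1.5 | 0.966 | 0.946 | 0.924 | 1.057 |
| 2 | 0.940 | 0.905 | 0.865 | 1.105 |
| 2.5 | 0.920 | 0.872 | 0.819 | 1.147 |
| 3 | 0.903 | 0.846 | 0.781 | 1.183 |

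Equal r in both arms gives 1.00. With r = 3 in the alcohol arm and 2 in the abstention arm, at k = 2.5, the ratio is 1.1875/1.2647 = 0.94.

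A fuller calculation used quarterly intervals over 6 years, censoring at first non-adherence and cumulative non-adherence probabilities. It agrees to within 0.01: 0.78 to 0.97 for the alcohol arm only, and 1.06 to 1.19 for the abstention arm only at r = 2. Raising mean non-adherence to 20% barely matters (0.81 to 0.91 at k = 2.5).

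**4. Comparators.** With the correct weight, each risk group's share among adherers is its original share × P(adherent) × 1/P(adherent). The 30/70 mix is restored in each arm and the hazard ratio is 1.00 in every scenario. Censoring with no weights, at 10% non-adherence and with risk-related stopping in the alcohol arm only, gives 0.97 to 1.00. In these scenarios the literal weight is therefore worse than none.

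**5. Error rate.** In 400 simulated null trials of 7,800 per scenario, with k = 2.5 and robust variance, the literal weights declared significant benefit in 28%, 55% and 85% of trials for r = 1.5, 2 and 3 in the alcohol arm only. Correct weights gave 1.5% to 3.7% across all scenarios simulated (nominal 2.5%).

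**The case against.** The best defence is that this is loose drafting. The section twice names the method by the probability of adherence, and it states the right target. A model for non-adherence gives adherence as its complement, and a weight that grows without bound as predicted stopping nears zero would probably be noticed. This is likely true, but it does not remove the contradiction. Nothing elsewhere in the document overrides the sentence.

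Second, the effect of stabilizing depends on the numerator, which the plan leaves open. If the numerator conditions on the same baseline covariates as the denominator, a fixed baseline risk group cancels out and the distortion computed above disappears. This stands as a limit on the figures. The literal weight would still be inverted for time-varying predictors.

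Third, a reader might infer that the plan builds in a large false benefit for alcohol. The documents do not support that. More extreme inputs can be chosen: stopping of 10% versus 2% a year in the alcohol arm, with event rates of 5% versus 1.6%, gives (0.3 × 1 × 0.05 + 0.7 × 5 × 0.016)/(0.3 + 3.5) = 0.0187, against 0.0262 in the abstention arm, a ratio of 0.71. No section supplies a fivefold stopping ratio, a threefold event-rate ratio, or stopping unrelated to risk in the abstention arm. With equal dependence there is no bias, and with the reverse pattern the error is a false harm. Section 7.4.5 makes the benefit direction plausible, but the document does not say whether stopping directed by the protocol counts as non-adherence.

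Fourth, simply adding censoring at first non-adherence would not be usable. Table 5.1 sets counselling triggers that a single lapse can meet in the abstention arm, and Section 7.4.5 allows temporary stops. Without a definition made for this analysis, much follow-up could be discarded. This also stands.

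**Conclusion.** The weight is wrong as written, because it contradicts the method's name and stated aim. It should be corrected. If it is followed literally, with a numerator that depends only on arm and time, the null hazard ratio moves to about 0.78 to 0.97, stays at 1.00, or moves to about 1.06 to 1.19, according to which arm has the stronger link between prognosis and stopping. The low end is beyond the design effect of 0.82. These sizes rest on the assumed prevalence, event hazard ratio and stopping ratios, on permanent stopping, and on 6 years of follow-up without loss. They show what the error can do and do not predict the trial's result.

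A reader might also infer that the trial's main conclusion is at risk. It is not. The intention-to-treat primary test (Section 8.1.1), the stopping rules (Section 8.1.3) and the sample size (Section 8.2) do not use these weights. One of several supporting analyses is affected, so this is a correction that should be made rather than a condition for the trial to proceed.

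**What to change.** Replace the sentence in Section 8.1.1 with a specification that states:
- the weight is the stabilized inverse of the cumulative probability of remaining adherent to time t;
- that probability is modelled within arm from named baseline and time-varying covariates;
- the stabilizing numerator is given explicitly, and if it includes baseline covariates, the weighted comparison adjusts for them;
- follow-up is censored at non-adherence as defined for this analysis, including whether stopping directed by the protocol or temporary stopping counts;
- a truncation rule applies to the weights, and the variance is robust to household clustering.

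The cost is a short text change plus agreement on the definition of non-adherence. It needs no new data and no change in sample size. It should be made before any unblinded analysis.

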6.3.6 FOLLOW-UP

After the baseline/randomization visit, participants will be seen in clinic for subsequent visits at 3 months, 6 months, 12 months, and then annually until close-out. Follow-up phone calls will occur at 2 weeks, 4 weeks, and 9 months during the first year, and every 3 months thereafter (except for annual

visits when participants are seen in clinic). See Table 6.1: Measures and Frequency for the sequence of events and special considerations (e.g., fasting visits) and the MOP regarding visit windows.

6.3.6.1 3 AND 6 MONTH IN-PERSON VISITS

- Contact information updated
- Blood pressure and pulse
- Blood draw for AST, ALT, GGT, HDL-C
- Timeline Followback (7-day)
- YBOCS-hd (3 items)
- Health Coaching (for adherence)
- Assessment for SAEs and MACH15 AEs
- Assessment for CVD outcomes

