To assess adherence during the first year of the trial, the change in high density lipoprotein cholesterol (HDL-C) will be compared over an approximate 6-month period between the two groups. Based on a two sample t-test, the mean change in the intervention arm to the mean change in the abstention arm will be compared. Since this analysis is based upon individual level change scores, there is no need to control for clinical site or other time-invariant covariates.

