Maximum Detectable Relative Risk for Diabetes (1% annual LTF and 10% non-adherence in single households, 9% in multiple participant households, ICC=0.005, proportion of households with ≥2 members=70%, proportion of additional household members eligible = 30%)		
	n=5,850 (25% baseline diabetes prevalence)	n=5,460 (30% baseline diabetes prevalence)
1.3%	0.72	0.71
1.5%	0.74	0.73
1.7%	0.75	0.74

During the vanguard phase, it will be essential to demonstrate that the minimum annual adherence rates are in place, to ensure adequate power. Hence, although HDL-C levels may or may not be part of the mechanism by which alcohol intake affects cardiovascular and diabetes risk, HDL-C is known to be an excellent marker of alcohol intake.¹⁹ Therefore, to assess adherence during the vanguard phase, we will compare the change in HDL-C over an approximately 6 month period between the two trial arms. Based on a two sample t-test for comparing the difference between the changes in the intervention and abstention groups, the minimum detectable change in HDL that could be expected for 80% power, assuming that there is no change in the abstention group, is given. We consider an assessment of adherence after 1,000 participants have been enrolled in total at the 7 vanguard clinical sites that are followed for at least 3 months. Assuming that the range of the standard deviation of the change in the HDL will be from 5 mg/dl to 8.5 mg/dl, corresponding to a 50% range around the median value, 6.7 mg/dl, reported by the meta-analysis by Rimm et al.,¹⁹ the minimum detectable difference between average changes in HDL cholesterol in the two groups in absolute values and in percents, for 80% power are given in the table above.

TABLE 8.4: CHANGE IN HIGH DENSITY LIPOPROTEIN-CHOLESTEROL

Standard deviation of the change in HDL-cholesterol	Minimum detectable change (n=1,000)	
	mg/dl	%
5	0.89	1.9
6.5	1.15	2.4
8	1.42	3.0
8.5	1.51	3.1

In the comprehensive meta-analysis of change in HDL-C in relation to alcohol intake based on 25 studies,¹⁹ it was found that a 41 g/day alcohol over an average of 4 weeks was related to a 5.1 mg/dl increase in HDL-C. For a dose of approximately 15 g/day, we would expect a 1.5 mg/dl increase in HDL-C over 3 months of observation in the first year. Clearly, we will have adequate power to detect this difference, even if the standard deviation for the change in HDL-C is on the highest end of what might be reasonably expected.

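### Section 8.1.1 gives a wrong reason for leaving the HDL-C adherence comparison unadjusted; the cost is mainly precision, and the target time point is not fixed

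*Combined protocol and SAP*

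**What the plan says.** **Test.** Section 8.1.1 states: "Based on a two sample t-test, the mean change in the intervention arm to the mean change in the abstention arm will be compared". The reason for adding nothing to the test follows: because the analysis uses each person's change score, "there is no need to control for clinical site or other time-invariant covariates". Section 8.2 repeats the two-sample t-test for the vanguard phase and sizes it from the SD of the raw change (Table 8.4). No baseline covariate, site term, household term or repeated-measures model is planned for HDL-C.

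**Time point.** In section 8.1.1 the change "will be compared over an approximate 6-month period between the two groups". Section 8.2 says "we will compare the change in HDL-C over an approximately 6 month period between the two trial arms", but places the assessment "after 1,000 participants have been enrolled in total at the 7 vanguard clinical sites that are followed for at least 3 months" and expects a 1.5 mg/dl rise over 3 months. Section 8.1.3 speaks of a difference in levels rather than changes.

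**Data available.** HDL-C is measured at the baseline visit (section 6.3.5). At the 3- and 6-month visits, section 6.3.6.1 lists "Blood draw for AST, ALT, GGT, HDL-C".

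**Use.** Under section 8.1.3 the result goes to the DSMB, with stopping to be discussed if the arms do not differ.

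**The concern.** A change score cancels whatever adds the same amount to a person's HDL-C at both visits. It does not cancel anything that alters the change itself. Baseline HDL-C is the clearest case: people with a high baseline value tend to fall and those with a low value tend to rise. Site could also act on change, since HDL-C is assayed in local laboratories (section 6.2.1.1) and only some sites run a daily-alcohol period before the washout (sections 5.4.1 and 6.3.3).

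The plan also departs from its own standard. Randomization is stratified by site (section 8.4), and members of one household are randomized as a unit (section 4.2). The primary analysis in section 8.1.1 accounts for both; the HDL-C test accounts for neither.

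This is the trial's planned biological check, at group level, that the two arms drink differently. Avoidable noise raises the chance that the DSMB is shown no difference when one exists. An unfixed time point leaves open which contrast it is shown, and what happens to participants who have only a 3-month value.

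**Working it through.** **Inputs from the documents.** 1,000 participants, balanced allocation, so 500 per arm; 80% power; SD of change 5 to 8.5 mg/dl with median 6.7; expected difference 1.5 mg/dl (all section 8.2, with the allocation from the précis). A two-sided 0.05 level is stated for the primary endpoint only and is assumed here for HDL-C.

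**Input assumed.** The between-person SD of HDL-C at one visit, S, is not in the documents. I use 12–16 mg/dl, and 10–18 as a wider range.

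**Step 1: reproduce Table 8.4.** Detectable difference = (1.960 + 0.842) × SD × √(2/500).

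| SD of change | Computed | Table 8.4 | Power for 1.5 mg/dl |
|---|---|---|---|
| 5 | 0.886 | 0.89 | 99.7% |
| 6.5 | 1.152 | 1.15 | 95.4% |
| 8 | 1.418 | 1.42 | 84.2% |
| 8.5 | 1.506 | 1.51 | 79.7% |

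All four rows agree, so the arithmetic is right for the planned test, and the two-sided level is confirmed (one-sided 0.05 would give 1.337 in the last row). Power at SD 8.5: 1.5 / (8.5 × √(2/500)) = 2.790; 2.790 − 1.960 = 0.830; Φ(0.830) = 79.7%.

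**Step 2: what differencing leaves behind.** With correlation ρ between baseline and follow-up and equal SDs, the slope of change on baseline is ρ − 1. It is zero only if ρ = 1. The SD of change fixes ρ = 1 − SD² / (2S²).

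**Step 3: adjust one follow-up value for baseline.** Variance of the raw change is 2S²(1 − ρ); residual variance after adjustment is S²(1 − ρ²); the ratio is (1 + ρ)/2. At SD of change 8.5:

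- S = 12: ρ = 1 − 72.25/288 = 0.749; SE ratio √0.8746 = 0.935; detectable difference 1.506 × 0.935 = 1.41.
- S = 13: ρ = 0.786; SE ratio 0.945; detectable difference 1.42; power for 1.5 rises from 79.7% to 84.0%.
- S = 16: ρ = 1 − 72.25/512 = 0.859; SE ratio 0.964; detectable difference 1.45.

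Over S = 10–18 and SD of change 5–8.5, the SE falls by about 1% to 9.5%. At the median SD of 6.7 and S = 13 it falls 3.4%, and power moves from 94.3% to 95.6%.

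**Step 4: average the 3- and 6-month values as well.** Variance is S²[(1 + ρ_f)/2 − ρ²], where ρ_f is the correlation between the two follow-up values. For S = 13 and SD of change 8.5, against the raw change score:

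- ρ_f = 0.786 (equal to ρ): SE ratio 0.802, a fall of about 20%.
- ρ_f = 0.95: SE ratio √[(0.975 − 0.618)/0.4275] = 0.914, a fall of about 9%.

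These totals include the 5.5% already gained from baseline. They require both samples in everyone, and they estimate a different quantity, the 3/6-month average.

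**Step 5: check by simulation.** With 4,000 simulated trials (S = 13, SD of change 8.5, equal correlations, true difference 1.5), every estimator averaged 1.51–1.52. Empirical SEs were 0.530 for raw change, 0.501 with baseline adjustment, and 0.423 with baseline adjustment and both samples. None is biased.

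**Not computable.** The within-household correlation of HDL-C change is not given. The ICC of 0.005 in section 8.2 belongs to the event endpoints.

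**The case against.** The strongest defence is that nothing here invalidates the comparison. Allocation is balanced within site in blocks of 4 and 8, so any laboratory drift at a site falls about equally on both arms, and regression to the mean is balanced by randomization too. That stands: this is a point about efficiency and a mistaken rationale. The documents do not show that drift differs by site; section 6.2.1.1 says only that analyses are local and laboratories are certified or controlled under local rules.

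The practical stakes are also modest. Power is short only at the most pessimistic SD; at the median it is about 94%. Section 8.1.3 calls for a discussion, not an automatic stop, and adherence is also followed by Timeline Followback and automated contacts, with direct biomarkers possible (section 5.4.2). That stands as well.

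A reader might infer more than the documents support:

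- **That baseline HDL-C is thrown away.** It is subtracted, with its coefficient fixed at 1. What is missing is baseline as a covariate.
- **That one of the two follow-up samples is dropped.** The documents never say which sample enters, or that participants with only a 3-month value are excluded. They show an ambiguous window, no more.
- **That using both samples would cut the variance by about a third at no cost.** That needs both samples in everyone, equal correlations between visits and an averaged estimand. Baseline follows a washout while both later samples are taken on assignment, so the later two may correlate more closely, which shrinks the gain. If adherence wanes, the average would exceed the 6-month contrast and could hide the problem this check is meant to find.

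**Conclusion.** The stated reason for not adjusting is incorrect and should go. The planned test remains unbiased; its cost is mainly some precision. At SD 8.5, where the detectable difference slightly exceeds the expected effect and a true 1.5 mg/dl would be missed about 20% of the time (100% − 79.7%), baseline adjustment alone brings the detectable difference to about 1.41–1.45 mg/dl. That rests on the assumed S of 12–16 and on equal SDs at the two visits. At smaller SDs power is already ample and the gain is slight. Ignoring households makes the standard error somewhat too small if members' changes are positively correlated, probably by little. The inconsistent time point is a separate gap, evident from the text without any assumption. Overall this is a minor but worthwhile refinement.

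**What to change.** 1. In section 8.1.1, delete the sentence saying that site and time-invariant covariates need no control.
2. In sections 8.1.1 and 8.2, replace the t-test with a model of HDL-C at 3 and 6 months on arm, visit, arm-by-visit, baseline HDL-C and site, with household-clustered standard errors.
3. Name the target time point, and align sections 8.1.1, 8.1.3 and 8.2 with it. One choice is the 6-month contrast, keeping 3-month values in the model so that participants without a 6-month value still contribute.
4. Report the arm difference with its 95% CI to the DSMB.
5. A 3/6-month average may be added as supportive, labelled as a different estimand.

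The cost is SAP wording and a few lines of code; every sample is already scheduled. Table 8.4 can stay if labelled as the unadjusted calculation, which ignores household clustering.
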